4.9.3. Secondary Efficacy Variables

In order to control the type I error, a sequential closed testing procedure will be employed with the sequence of endpoints defined as in Section 4.9.1.3 above. Testing of secondary endpoints will be performed only if the treatment comparison of the primary analysis of the primary endpoint is statistically significant (p < 0.05) for both ISIS 678354 80-mg and 50-mg treatment groups. Testing of the secondary endpoints will be conducted according to the following sequence: if the primary analysis of the first secondary endpoint (comparison of percent change in fasting TG from Baseline to Month 12 between ISIS 678354 80-mg treatment group and pooled placebo in FAS) is statistically significant (p < 0.05) then the second ary endpoint (comparison of percent change in fasting apoC-III from Baseline to the primary analysis time point between ISIS 678354 80-mg treatment group and pooled placebo in FAS) will be tested. However, if the treatment comparison based on the first secondary endpoint is not statistically significant, then all endpoints of lower rank will be considered exploratory. This process is repeated with each subsequent secondary endpoint.

4.9.3.1. Percentage Change from Baseline in Fasting TG at Month 12

The percent change in fasting TG from Baseline to Month 12 in the FAS will be analyzed in the same way as the primary analysis of the primary endpoint. The intercurrent events will be handled using the Treatment Policy strategy.

A 2-dimensional tipping-point analysis will be conducted in the FAS as a sensitivity analysis.

Descriptive statistics and cumulative distribution curves will be provided for observed fasting TG levels and percent change in TG in each treatment group at Month 12.

4.9.3.2. Proportion of Patients who Achieve ≥ 40% Reduction in Fasting TG from Baseline at the Primary Analysis Time Point

The proportion of patients who achieve $\geq 40\%$ reduction in fasting TG from Baseline to the primary analysis time point in the FAS will be compared between each ISIS 678354 treatment group and placebo group using a logistic regression model with the 2 randomization stratification factors and treatment group as the factors, and nature log-transformed baseline fasting TG as a covariate. Missing TG values will be imputed using the same multiple imputation method as the primary analysis of the primary endpoint. The estimates from the fitted model for each of the 100 imputed datasets will be combined to provide an overall odds ratio with corresponding confidence intervals and p-value. The intercurrent events will be handled using the Treatment Policy strategy.

Sensitivity Analysis 1: An additional analysis will be conducted in the FAS, in which all patients who have missing data and discontinue treatment before Week 23 will be considered as non-responders.

Sensitivity Analysis 2: A 2-dimensional tipping-point analysis will be conducted in the FAS using the imputed data based on the primary imputation approach as described in Section 4.9.1.2 in the SAP.

4.9.3.3. Percentage Change from Baseline in Fasting apoC-III, apoB-48, and non-HDL-C at Primary Analysis Time Point (Months 6) and Month 12

The percent change in fasting apoC-III, apoB-48, and non-HDL-C from Baseline to the primary analysis time point and Month 12 in the FAS will be analyzed in the same way as the primary analysis of the primary endpoint. The same multiple imputation method as the primary analysis of the primary endpoint will be used for imputing missing data. The intercurrent events will be handled using the Treatment Policy strategy. A 2-dimensional tipping-point analysis will be conducted in the FAS as a sensitivity analysis for each parameter.

4.9.3.4. Proportion of Patients who Achieve Fasting TG ≤ 880 mg/dL at Primary Analysis Time Point

The proportion of patients who achieve fasting $TG \le 880 \text{ mg/dL}$ at the primary analysis time point will be analyzed in the same way as the proportion of patients who achieve $\ge 40\%$ reduction in fasting TG. Missing TG values will be imputed using the same multiple imputation method as the primary analysis of the primary endpoint. The analysis will be conducted in the subset of FAS with baseline fasting TG > 880 mg/dL. The intercurrent events will be handled using the Treatment Policy strategy.

Sensitivity Analysis 1: An additional analysis will be conducted in the subset of FAS with baseline fasting TG > 880 mg/dL, in which all patients who have missing data and discontinue treatment before Week 23 will be considered as non-responders.

Sensitivity Analysis 2: A 2-dimensional tipping-point analysis will be conducted in the subset of FAS with baseline fasting TG > 880 mg/dL using the imputed data based on the primary imputation approach as described in Section 4.9.1.2 in the SAP.

4.9.3.5. Adjudicated Acute Pancreatitis Event Rate from Week 1 to Week 53 in the Subset of FAS with a prior history of pancreatitis within 10 years prior to Screening

All AEs and SAEs that occur during the study that are consistent with an event of acute pancreatitis will be adjudicated by a blinded, independent committee according to the Atlanta classification of acute pancreatitis and as outlined in the Acute Pancreatitis Adjudication Committee (PAC) Charter. These events will be categorized by the various criteria to be one of the following: 1) documented pancreatitis, 2) probable pancreatitis, 3) possible pancreatitis, 4) unable to adjudicate and

Statistical Analysis Plan

5) no diagnosis of acute pancreatitis. In the event of any discrepancies between the categories in this SAP and the final data transfer, the categories in the final data transfer will be used. For the purposes of data analysis, events that are documented, probable or possible are to be considered adjudicated acute pancreatitis. A listing will be provided to display each adjudicator's and the final adjudication committee's classification results for each event. The number and percentage of subjects and the number of events within each classification, by each adjudicator and by final adjudication committee respectively, will be summarized. In addition, the number and percentage of cases where the adjudicator's individual categorization of the event was discordant will be provided. The summaries be conducted in the FAS.

The adjudicated acute pancreatitis event rate from Week 1 to Week 53 in the subset of FAS with a prior history of pancreatitis within 10 years prior to Screening will be compared between pooled ISIS 678354 treatment and placebo group using a Negative Binomial regression model with the treatment group and previous treatment with volanesorsen (yes/no) as the factors, and number of adjudicated acute pancreatitis events in 5 years prior to the enrollment, i.e., events occurred within 1826 days (calculated by 365.25 times 5 and rounded to integer) before the first dose date and up to the first dose date and time, as a covariate. The logarithm of time in year that each patient was observed from Week 1 to Week 53 will be used as an offset variable. From the models, the least squares mean rate and standard error for each treatment group as well as, the mean rate ratio relative to the placebo group and corresponding 95% confidence intervals will be estimated. The p-value of Wald-based chi-square test will also be reported.

Week 53 is defined as Day 379 (scheduled visit day plus a 14-day window) or last contact date within the study, whichever is earlier. If patients have intercurrent event(s) before Week 53, the Treatment Policy strategy will be implemented, the pancreatitis events occurred post intercurrent events will continue to be collected. All adjudicated pancreatitis events including those post the intercurrent events will be included in the analysis. For patients who discontinued the treatment early and were lost to follow-up before Week 53, the pancreatitis event rate will be adjusted by the length of observation time in the analysis model.

The sample SAS code for the ANCOVA model can be found below:

- * TRTN = Treatment group: 0=Placebo, 1= ISIS 678354 50 mg or ISIS 678354 80 mg
- * VOLAN= Previous treatment with Volanesorsen: 0= No, 1= Yes
- * NUMEVENT = number of adjudicated acute pancreatitis events
- * NUM5YEAR = number of adjudicated acute pancreatitis events in 5 years prior to the enrollment

If the Negative Binomial regression model does not converge, a Poisson regression model with Pearson chi-square scaling of standard errors to account for potential overdispersion will be used instead of the Negative Binomial regression model. The model will include the same factors and covariate as the Negative Binomial regression model.

If one treatment group has no event, instead of using Negative Binomial or Poisson regression model on the number of events, the proportion of patients with adjudicated acute pancreatitis will be compared between pooled ISIS 678354 treatment group and placebo group using a Fisher's Exact test. The odds ratio, corresponding 95% CI, and p-value will be reported.

Additional dot plots by treatment group will be provided for pancreatitis attacks, grouped by number of previous attacks in the last 5 years.

4.9.3.6. Adjudicated Acute Pancreatitis Event Rate from Week 1 to Week 53 in the FAS

The data will be analyzed in the same way as described in Section 4.9.3.5.

Additional dot plots will be by treatment group provided for pancreatitis attacks, grouped by number of previous attacks in the last 5 years.

4.9.3.7. Adjudicated Acute Pancreatitis Event Rate from Week 13 to Week 53 in the Subset of FAS with a prior history of pancreatitis within 10 years prior to Screening

The data will be analyzed in the same way as described in Section 4.9.3.5.

4.9.3.8. Adjudicated Acute Pancreatitis Event Rate from Week 13 to Week 53 in the FAS

The data will be analyzed in the same way as described in Section 4.9.3.5.

4.9.3.9. Adjudicated Acute Pancreatitis Event Rate from Week 1 to Week 53 in the Subset of FAS with ≥ 2 Events of Adjudicated Acute Pancreatitis in 5 years Prior to Enrollment

The data will be analyzed in the same way as described in Section 4.9.3.5. The period of 5 years prior to enrollment spans from 1826 days before the first dose date and up to the first dose date and time.

4.9.3.10. Adjudicated Acute Pancreatitis Event Rate from Week 13 to Week 53 in the Subset of FAS with ≥ 2 Events of Adjudicated Acute Pancreatitis in 5 years Prior to Enrollment

The data will be analyzed in the same way as described in Section 4.9.3.5.

4.9.3.11. Proportion of Patients who Achieve Fasting TG ≥ 70% Reduction from Baseline at Primary Analysis Time Point

The proportion of patients who achieve fasting $TG \ge 70\%$ reduction at the primary analysis time point in the FAS will be analyzed in the same way as the proportion of patients who achieve $\ge 40\%$ reduction in fasting TG. Missing TG values will be imputed using the same multiple imputation method as the primary analysis of the primary endpoint. The intercurrent events will be handled using the Treatment Policy strategy.

Sensitivity Analysis 1: An additional analysis will be conducted in the FAS, in which all patients who have missing data and discontinue treatment before Week 23 will be considered as non-responders.

Sensitivity Analysis 2: A 2-dimensional tipping-point analysis will be conducted in the FAS using the imputed data based on the primary imputation approach as described in Section 4.9.1.2 in the SAP.

4.9.3.12. Proportion of Patients who Achieve Fasting TG ≤ 500 mg/dL at Primary Analysis Time Point

The proportion of patients who achieve fasting $TG \le 500 \text{ mg/dL}$ at the primary analysis time point will be analyzed in the same way as the proportion of patients who achieve $\ge 40\%$ reduction in fasting TG. Missing TG values will be imputed using the same multiple imputation method as the primary analysis of the primary endpoint. The analysis will be conducted in the subset of FAS with baseline fating TG > 500 mg/dL. The intercurrent events will be handled using the Treatment Policy strategy.

Sensitivity Analysis 1: An additional analysis will be conducted in the subset of FAS with baseline fasting TG > 500 mg/dL, in which all patients who have missing data and discontinue treatment before Week 23 will be considered as non-responders.

Sensitivity Analysis 2: A 2-dimensional tipping-point analysis will be conducted in the subset of FAS with baseline fasting TG > 500 mg/dL using the imputed data based on the primary imputation approach as described in Section 4.9.1.2 in the SAP.

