For each of the 100 imputed datasets, the endpoint will be compared between ISIS 678354 treatment groups and pooled placebo using an ANCOVA model for continuous endpoints or logistic regression for binary endpoints as described in the primary analysis for each endpoint. The estimates from the 100 fitted models will be combined to provide an overall estimate with corresponding confidence intervals and p-value (Little & Rubin 2002)

The following pseudo SAS code will be used to estimate corresponding confidence intervals and p-value:

```
proc mianalyze data=diff;
    modeleffects estimate;
    stderr stderr;
```

run;

For the continuous endpoints, the treatment difference and the corresponding 95% CI will be presented. For the analyses using logistic regression, the odds ratio and the corresponding 95% CI will be presented.

Missing values at Months 3 and 12 and other lipid parameters will be imputed in a similar way to the primary analysis time point.

Only observed lipid data will be displayed in the data listings.

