4.11.3.2. Treatment Response Rate

The following treatment response rates between ISIS 678354 treatment group (ISIS 678354 80 mg, ISIS 678354 50 mg) and placebo groups will be compared as exploratory analyses using logistic regression with the treatment group, two randomization stratification factors as the factors, and nature log-transformed baseline fasting TG as a covariate in the FAS.

- Proportion of patients who achieve fasting $TG \ge 40\%$ Reduction from Baseline at Months 3 and 12
- Proportion of patients who achieve fasting TG \ge 70% Reduction from Baseline at Months 3 and 12
- Proportion of patients who achieve fasting TG \leq 880 mg/dL at Months 3 and 12 in the subset of FAS with baseline fasting TG > 880 mg/dL
- Proportion of patients who achieve fasting TG \leq 500 mg/dL at Months 3 and 12 in the subset of FAS with baseline fasting TG > 500 mg/dL

Missing values will be handled using the same multiple imputation method as the primary analysis of the primary endpoint.

ISIS 678354-CS3

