4.12. Determination of Sample Size

Based upon prior clinical trial experience with FCS patients, the SD of the percent change from Baseline in TGs is approximately 46%. With 14 patients in each ISIS 678354 treatment group and 14 in the pooled placebo group, there would be a 90% power to detect a 60% difference between each ISIS 678354 treatment group and pooled placebo group at an alpha level of 0.05 (two-sided), assuming 60% reduction in the ISIS 678354 treatment patients and no change in the placebo patients. Approximately 60 patients will be enrolled in this trial to account for potential early dropouts and to facilitate general safety evaluation.

Eligible patients will be randomized 1:1 to Cohort A or Cohort B and each cohort further randomized 2:1 (ISIS 678354:placebo) and stratified for:

- Prior history of pancreatitis within 10 years prior to Screening* vs. no history of pancreatitis or no history within 10 years prior to Screening
- Previous treatment with volanesorsen
- * History of pancreatitis is defined as a recorded diagnosis of acute pancreatitis or hospitalization for severe abdominal pain consistent with acute pancreatitis and for which no alternate diagnosis was made

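### The ≥ 70% TG-reduction endpoint has no rule for a placebo arm without responders; in that case the planned logistic analysis gives a p-value near 1 and an odds ratio that cannot be interpreted

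*Combined protocol and SAP*

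**What the plan says.** SAP 4.9.3.2 compares the ≥ 40% reduction responder proportions "using a logistic regression model with the 2 randomization stratification factors and treatment group as the factors", with log baseline TG as covariate. The 100 fits are "combined to provide an overall odds ratio with corresponding confidence intervals and p-value". For ≥ 70% reduction, SAP 4.9.3.11 says that the proportion "at the primary analysis time point in the FAS will be analyzed in the same way as the proportion of patients who achieve" the 40% reduction. Protocol 10.6.3.2 gives the same model.

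SAP 4.9.1.2 describes the fit to each imputed data set as "using an ANCOVA model for continuous endpoints or logistic regression for binary endpoints". Its PROC MIANALYZE code takes only an estimate and a standard error. On reporting it says: "For the analyses using logistic regression, the odds ratio and the corresponding 95% CI will be presented".

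SAP 4.11.3.2 reuses the model at Months 3 and 12, where the active and "placebo groups will be compared as exploratory analyses using logistic regression with the treatment group" and the same covariates.

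The only rule for an arm without events is in the pancreatitis analysis of SAP 4.9.3.5: "If one treatment group has no event, instead of using Negative Binomial or Poisson regression model", patients with an event are compared by Fisher's exact test. That section also has the only non-convergence rule. Neither document has a counterpart for the TG responder endpoints. Their sensitivity analyses (non-responder imputation and tipping point) do not address an empty cell.

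**The concern.** A 70% fall in TG should be rare on placebo, and the placebo group is small, so a placebo arm with no responders is a realistic outcome. Ordinary logistic regression then has no finite maximum-likelihood estimate for the treatment effect: the log odds ratio grows with each iteration and its standard error grows much faster. A test built from their ratio moves towards p = 1 however strong the effect is.

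Followed as written, the plan would report a clear difference as non-significant, with an odds ratio and 95% CI that carry no information. The SAP anticipates this situation for pancreatitis but not here.

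**Working it through.** **1. Inputs.** SAP 4.12 states that "the SD of the percent change from Baseline in TGs is approximately 46"%, with a mean change of −60% on active and 0 on placebo, and two-sided alpha of 0.05. Sixty patients randomised 1:1 to two cohorts and 2:1 within each give 20 / 20 / 20. The lay summary gives actual numbers of 22 (80 mg), 21 (50 mg) and 23 (placebo).

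**2. The plan's own figure.** A two-sample t-test with 14 per group, difference 60 and SD 46 has 91.3% power (noncentral t, 26 df), close to the stated 90%. The documents give no placebo responder rate and no power for the ≥ 70% endpoint.

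**3. Probability of an empty placebo arm.** This is (1 − p)^n, where p is the placebo response rate.
- Normal: p = Φ(−70/46) = 0.064. (1 − 0.064)^20 = 0.27; with n = 23, 0.22.
- Log-normal TG ratio with mean 1 and SD 0.46: σ = √ln(1 + 0.46²) = 0.438. p = Φ((ln 0.3 + σ²/2)/σ) = Φ(−2.53) = 0.0057. (1 − 0.0057)^20 = 0.89; with n = 23, 0.88.
- SD 35: p = 0.0228 (normal) or 0.00037 (log-normal), giving 0.63 or 0.99.
- SD 60: p = 0.1217 (normal) or 0.0291 (log-normal), giving 0.075 or 0.55.

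For ≥ 40% reduction at SD 46, the same calculation gives only 0.014 to 0.023.

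**4. What the test does with 0/20 on placebo** (unadjusted 2×2 tables; Firth LR is the penalised likelihood-ratio test):

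| Active | Wald p, 8 iterations | Wald p, 25 iterations | Firth-Wald | Firth LR | Fisher |
|---|---|---|---|---|---|
| 6/20 | 0.71 | 1.0 | 0.059 | 0.008 | 0.020 |
| 8/20 | 0.69 | 1.0 | 0.030 | 0.001 | 0.003 |
| 10/20 | 0.68 | 1.0 | 0.015 | 0.0001 | 0.0004 |

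For 10/20 at 8 iterations the log odds ratio is 9.20 with SE 22.3, so the CI for the odds ratio runs from about 1e-15 to 9e22. Firth gives an odds ratio of 41 (2.0 to 828). For any active count from 1 to 19, the smallest Wald p at 8 iterations is 0.59.

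**5. Power at a true 60% reduction** (exact binomial sums, 20 v 20, unadjusted). The last column is the probability that the placebo arm is empty and Fisher p < 0.05.

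| Model | Wald | Firth-Wald | Firth LR | Fisher | Empty and Fisher p < 0.05 |
|---|---|---|---|---|---|
| Normal | 49% | 64% | 79% | 68% | 0.26 |
| Log-normal, CV 46% in each arm | 5% | 51% | 91% | 81% | 0.75 |
| Log-normal, SD 46 points in each arm | 11% | 98% | 99.9% | 99.6% | 0.89 |

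**6. With the SAP's covariates.** The check used 2000 simulated three-arm trials per scenario, with illustrative covariates of no effect and no missing data. Wald rejected in none of the 547, 1795 and 1774 trials with an empty placebo arm.

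**7. Does imputation fill the cell?** One observed visit of the three is enough to define the Month 6 value (SAP 4.2.3), and Protocol 10.6.3.1 expects little missing data. An empty arm would therefore normally be empty in all 100 data sets. Even when 5% to 80% of the data sets contain one placebo responder (8/20 active), the pooled p stays above 0.99. It becomes usable (0.024) only when all of them do.

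**The case against.** **The formal consequence is small.** This stands. The endpoint is 17th (80 mg) and 21st (50 mg) in the sequence of 28. Both are confirmatory only if both doses succeed on the primary endpoint and every earlier comparison succeeds. The lay summary says that 50 mg did not. A reader might infer that a failure at position 17 wrongly made positions 18 to 28 exploratory in this trial. The documents do not support that, because the secondary family was already exploratory.

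**Readers would see the counts, and the SAP allows departures.** This also stands in part. SAP 4.2.1 requires counts and percentages for categorical data, so an empty arm would show beside the odd estimate. SAP section 1 lets deviations be justified in the study report. But counts are not a test, and a method chosen after seeing the empty cell is weaker than one fixed beforehand.

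**The probabilities rest on assumed shapes.** Correct: SAP 4.12 gives a mean and an SD, not a distribution. The normal model also puts mass below −100% change, which is impossible: 1.5 of the 6.4 percentage points of placebo response and 19 of the 41 points of active response. Its power figures rest partly on those values, although removing them would not make an empty arm less likely.

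**Saying that the test can never reject is too strong.** Agreed. The SAP names neither a Wald test nor an iteration limit for these models; Wald-type is inferred from pooling an estimate and its SE. A fit stopped after about 4 iterations could give p < 0.05 with a very high active response, as an artefact of where it stopped.

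**Conclusion.** The gap is real. With no placebo responder and a fit iterated to ordinary convergence, the planned analysis of ≥ 70% reduction does not reject, and the odds ratio and CI that the SAP commits to presenting are uninterpretable. On the planning mean and SD with 20 placebo patients, the probability of that case is 0.27 (normal) or 0.89 (log-normal), and 0.075 to 0.99 over SDs of 35 to 60.

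The effect is on the reported odds ratio, CI and nominal p-value at Month 6 and, through SAP 4.11.3.2, at Months 3 and 12. Two stronger readings are not supported. The documents give no responder counts, so nothing shows that separation actually occurred. Nor does the likelihood carry over to ≥ 40% reduction, where an empty placebo arm is improbable. It should be corrected because the stated rule can give a wrong result and the remedy is cheap.

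**What to change.** State in SAP 4.9.3.2, which 4.9.3.4, 4.9.3.11 and 4.9.3.12 reuse, and in 4.11.3.2, that the responder models are fitted by Firth penalised-likelihood logistic regression. Keep the same covariates, apply it to every imputed data set whether separated or not, and pool by the existing Rubin's rules. The method then does not depend on the data. Optionally, take the p-value from the penalised likelihood-ratio test combined over imputations, with a pooled penalised profile-likelihood CI. These are different pooling rules, so agreement between p-value and CI should not be promised. If the analysis has already been run, report the Firth result as a documented deviation under SAP section 1.

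The cost is two sentences and one model option, with no new data. Downsides:
- Firth with Wald pooling is conservative in sparse tables: 6/20 v 0/20 gives p = 0.059 against Fisher 0.020, and power is 51% against 81% in the log-normal CV 46% model.
- The odds ratio is shrunk.
- The likelihood-ratio version needs pooling code beyond the SAP's PROC MIANALYZE step.

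At ≥ 40% reduction, which the change also covers, the exact unadjusted normal-model calculation shows no power loss: 85.6% Wald, 86.4% Firth-Wald and 87.0% Firth LR.
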